### 4.2 Scientific Rationale for Study Design

#### 4.2.1 Rationale for Selection of Participant Population

AZD0780 is a potential first-in-class oral small molecule PCSK9 inhibitor, and this study is part of a program to confirm if AZD0780 will lower cardiovascular risk in both primary and secondary prevention, when taken once daily along with SoC.

The population included in this study comprises male or female participants of non-childbearing potential, 18 to 75 years of age with a fasting LDL-C of  $\geq 70$  (1.8 mmol/L) and  $< 190$  mg/dL (4.9 mmol/L) at screening. Each participant should meet all the inclusion criteria and none of the exclusion criteria to be assigned/randomized to a study intervention. Under no circumstances can there be exceptions to this rule. Participants who do not meet the entry requirements are screen failures (Section 5.4).

#### 4.2.2 Rationale for Selection of Primary Endpoint

Statins are the first-line therapy for lowering of LDL-C recommended by the latest dyslipidemia guidelines (Mach et al 2020; Reiter-Brennan et al 2020). Reduction of LDL-C levels by statins leads to significant reduction in cardiovascular events including coronary artery disease and other cardiovascular related deaths (Collins et al 2016). However, despite the substantial benefits of statin therapy, many patients do not reach LDL-C target levels. Current guidelines call for LDL-C to be lowered  $\geq 50\%$  with maximally tolerated statins in patients with existing atherosclerotic CVD (Atar et al 2021). Additional evidence demonstrates that aggressively lowering LDL-C levels to  $< 40$  mg/dL lowers CVD risk in a wider range of patients (Marston et al 2021). This underscores the medical need for developing new cost-effective LDL-C lowering medicines to achieve the most recent dyslipidemia guidelines for the prevention of CVD.

#### 4.2.3 Rationale for Selection of Comparator

The comparator in this study is placebo. Both AZD0780 and placebo will be administered on top of moderate or high-intensity statin therapy; therefore, the treatment of the placebo group will correspond to current SoC for participants with dyslipidemia.

The use of placebo will allow for a double-blinded treatment period and to provide a control arm, so as to enable a continued comparison of efficacy, in particular the comparison of dose-dependent change in LDL-C after oral administration of multiple doses of AZD0780, and to act as a comparator to contextualize safety observations.

#### 4.2.4 Rationale for Selection of Study Duration

The treatment length in the study is 12 weeks. Based on data from a MAD study (Study D7960C00001), steady state in plasma exposure of AZD0780 was reached after one week of once daily dosing with AZD0780, while steady state in the LDL-C lowering effect was reached within approximately 2 weeks of treatment. With a treatment length of 12 weeks participants are predicted to be at least 10 weeks on stable LDL-C lowering effect, allowing for a robust assessment of the lipid effects of AZD0780. Twelve weeks of dosing is also predicted to allow for a robust assessment of safety, tolerability and the PK of AZD0780 to guide dose selection for further clinical development of AZD0780.

#### 4.3 Justification for Dose

Single doses of AZD0780 up to **[REDACTED]** mg and multiple doses of AZD0780 up to **[REDACTED]** mg once daily for up to 4 weeks of dosing have been evaluated and shown to be well tolerated in participants with elevated LDL-C (ongoing Study D7960C00001). The doses for the current study were selected based on the observed safety, tolerability, and LDL-C reducing data from the MAD cohorts.

The mid and high dose, planned to be **[REDACTED]** mg and **[REDACTED]** mg AZD0780, were selected to reach close to maximum achievable reduction in LDL-C. The aim with the highest dose (**[REDACTED]** mg) is to show that an increase above the **[REDACTED]** mg dose will not result in any further clinically significant reduction in LDL-C compared to **[REDACTED]** mg AZD0780. Due to the uncertainty in dose/exposure response at doses below **[REDACTED]** mg, two lower doses were also selected for this study, **[REDACTED]** mg and **[REDACTED]** mg. The aim is to have at least one dose that shows a clinically significant lower LDL-C reduction as compared to the **[REDACTED]** mg and **[REDACTED]** mg doses. The 2 mid doses, **[REDACTED]** mg and **[REDACTED]** mg, were thus selected for the potential to be in the therapeutic dose range.

Prior to the start of dosing in the current study, safety and tolerability data from multiple dosing of **[REDACTED]** mg AZD0780 once daily for 4 weeks will have been evaluated in the ongoing Study D7960C00001 in participants with elevated LDL-C.

#### 4.4 End-of-study Definition

For the purpose of Clinical Trial Transparency the definition of the end of the study differs under FDA and EU regulatory requirements:

European Union requirements define study completion as the last visit of the last subject for any protocol related activity.

Food and Drug Administration requirements defines 2 completion dates:

Primary Completion Date – the date that the final participant is examined or receives an intervention for the purposes of final collection of data for the primary outcome measure, whether the clinical study concluded according to the pre-specified protocol or was terminated. In the case of clinical studies with more than one primary outcome measure with different completion dates, this term refers to the date on which data collection is completed for all of the primary outcomes.

Study Completion Date – the date the final participant is examined or receives an intervention for purposes of final collection of data for the primary and secondary outcome measures and AEs (for example, last participant's last visit), whether the clinical study concludes according to the pre-specified protocol or is terminated.

A participant is considered to have completed the study if they have completed all phases of the study including the last visit.

## **5 STUDY POPULATION**

Participants will be males and females of non-childbearing potential (ie, postmenopausal or surgically sterile), aged 18 to 75 years (inclusive), with a fasting LDL-C  $\geq$  70 mg/dL (1.8 mmol/L) and  $<$  190 mg/dL (4.9 mmol/L), fasting triglycerides  $<$  400 mg/dL ( $<$  4.52 mmol/L), and have a BMI at or above 19.0 kg/m^2.

Prospective approval of protocol deviations to recruitment and enrollment criteria, also known as protocol waivers or exemptions, is not permitted.

Each participant should meet all the inclusion criteria and none of the exclusion criteria for this study. Under no circumstances can there be exceptions to this rule.

### **5.1 Inclusion Criteria**

Participants are eligible to be included in the study only if all of the following criteria apply:

#### **Age**

- 1 Males, and females of non-childbearing potential, 18 to 75 years of age, inclusive, at the time of signing the informed consent.

#### **Type of Participant and Disease Characteristics**

- 2 Participants with a fasting LDL-C  $\geq$  70 mg/dL (1.8 mmol/L) and  $<$  190 mg/dL (4.9 mmol/L) at screening.
- 3 Participants with fasting triglycerides  $<$  400 mg/dL ( $<$  4.52 mmol/L) at screening.
- 4 Should be receiving moderate or high-intensity statin therapy for  $\geq$  2 months prior to screening, according to ACC/AHA guidelines on blood cholesterol management, or to local guidelines, eg, Japanese Atherosclerosis Society guidelines.
- 5 There should be no planned medication or dose change during study participation.

#### **Weight**

- 6 Body mass index at or above 19.0 kg/m^2.

#### **Sex**

- 7 Male participants:
  - (a) Males must be surgically sterile or using, in conjunction with their female partner, a highly effective method of contraception for the duration of the study (from the time they sign consent) and for 3 months after the final follow up visit to prevent pregnancy in a partner. Acceptable methods of contraception include birth control pills, injections, implants, or patches, IUDs, tubal ligation/occlusion, and vasectomy. A barrier method is not necessary if the female partner is sterilized. Male study participants must not donate or bank sperm during this same time

8 Female participants:

- (a) Female participants must not be pregnant and must have a negative pregnancy test at screening and randomization, must not be lactating, and must not be of childbearing potential. Women not of childbearing potential are defined as women who are either permanently sterilized (hysterectomy, bilateral oophorectomy, or bilateral salpingectomy), or who are postmenopausal. Women will be considered postmenopausal if they have been amenorrhoeic for 12 months prior to the planned date of randomization without an alternative medical cause. The following age-specific requirements apply:
  - (i) Women < 50 years of age would be considered postmenopausal if they have been amenorrhoeic for 12 months or more following cessation of exogenous hormonal treatment and FSH levels in the postmenopausal range.
  - (ii) Women  $\geq$  50 years of age would be considered postmenopausal if they have been amenorrhoeic for 12 months or more following cessation of all exogenous hormonal treatment.

9 Restrictions for male participants

- (a) All male participants should avoid fathering a child by either true abstinence or by using (together with their female partner/spouse) a highly effective contraception form of birth control in combination with a barrier method, starting from the time of study intervention administration until 3 months after the Final Follow-Up visit. Acceptable methods of preventing pregnancy include birth control pills, injections, implants, or patches, IUDs, tubal ligation/occlusion, and vasectomy.
- (b) Male participants who have been sterilized are required to use 1 barrier method of contraception (condom) from the time of study intervention administration until after the Final Follow-Up Visit. A barrier method is not necessary if the female partner is sterilized.
- (c) Male participants should not donate sperm for the duration of the study and for at least 3 months post last follow-up visit.

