Potential risk of clinical significance	Summary of data/rationale for risk	Mitigation strategy
Dyspnea	
In in vitro studies, AZD0780 is an adenosine transport inhibitor (IC50 ~15 <math>\mu</math>M). Inhibition of adenosine transporters can result in dyspnea and bronchospasm in patients with respiratory disease. In addition, inhibition of <math>\alpha</math>1A adrenoceptors (Ki=18 <math>\mu</math>M and functional IC50 ~47 <math>\mu</math>M) identified in AZD0780 in vitro studies, can result in dyspnea, observed in clinical trials with <math>\alpha</math>-adrenoceptor antagonists.
 
The respiratory safety pharmacology study with AZD0780 in rats did not show any effect on respiratory parameters as assessed by plethysmography.
	
 
Exclusion of participants with any uncontrolled or serious disease, or any medical (eg, known major active infection or major hematological, renal, metabolic, gastrointestinal, respiratory, or endocrine dysfunction) or surgical condition that, in the opinion of the investigator, may either interfere with participation in the clinical study and/or put the participant at significant risk (exclusion criterion 3).
 
Adverse events, physical examinations and vital signs, including respiratory rate and pulse oximetry, will be monitored throughout the study.
 
Individual stopping criteria have been defined to consider exacerbation of respiratory disease.
 

Effects on Reproduction	
AZD0780 was shown to be an antagonist of the serotonin receptor 5-hydroxytryptamine receptor 2B (5-HT2B). Possible adverse effects of 5-HT2B receptor antagonism include developmental toxicity (based on complete knockout).
 
AZD0780 inhibits <math>\alpha</math>1A adrenoceptor. In clinical studies <math>\alpha</math>1A adrenoceptor antagonism has resulted in a reduction of uterine and vas deferens contractility and AE reports of abnormal ejaculation.
 
Nonclinical developmental toxicity studies for AZD0780 have not yet been performed.
	
 
Women of childbearing potential will be excluded from the study (inclusion criteria 1 and 8).
 
Reproductive restrictions will be in place throughout the study.
 

Potential risk of clinical significance	Summary of data/rationale for risk	Mitigation strategy

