#### **8.3.10.2    Paternal Exposure**

Male participants should refrain from fathering a child or donating sperm during the study and for 3 months following the last follow-up visit.

Pregnancy of the participant's partners is not considered to be an AE. However, the outcome of all pregnancies (spontaneous miscarriage, elective termination, ectopic pregnancy, normal birth or congenital anomaly), occurring from the date of the first dose until 10 months after the last dose should, if possible, be followed up and documented in the Pregnancy Report Form.

Consent from the pregnant partner must be obtained before the Pregnancy Report Form is completed.

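### Inclusion criteria 7(a), 9(a) and 9(b) contradict each other on male contraception in three respects: abstinence, when the barrier ends for sterilised men, and the waiver for a sterilised partner

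*Protocol*

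**What the plan says.** Section 5 of the protocol requires each participant to satisfy every inclusion criterion and rules out waivers and exceptions, so criteria 7 and 9 apply together.

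- **Criterion 7(a):** "Males must be surgically sterile or using, in conjunction with their female partner, a highly effective method of contraception", running "for the duration of the study (from the time they sign consent) and for 3 months after the final follow up visit". Abstinence is not mentioned. No barrier is asked for, yet the paragraph adds that one is unnecessary when the female partner is sterilised.
- **Criterion 9(a):** "All male participants should avoid fathering a child by either true abstinence or by using (together with their female partner/spouse") a highly effective method "in combination with a barrier method, starting from the time of study intervention administration until 3 months after the Final Follow-Up visit". Its list of methods includes vasectomy and tubal ligation. It has no waiver for a sterilised partner.
- **Criterion 9(b):** "Male participants who have been sterilized are required to use 1 barrier method of contraception (condom) from the time of study intervention administration". The requirement lasts until after the final follow-up visit, with no 3-month extension, and is waived if the partner is sterilised.
- **Section 8.3.10.2:** "Male participants should refrain from fathering a child or donating sperm during the study and for 3 months following the last follow-up visit". It has no separate rule for sterilised men and does not address barriers.

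Table 2 gives the background: "Nonclinical developmental toxicity studies for AZD0780 have not yet been performed". It names two mitigations for reproductive effects, the exclusion of women of childbearing potential and reproductive restrictions during the study.

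**The concern.** Because the criteria are cumulative, a site may not pick the paragraph that suits the man in front of it. Where one paragraph accepts or releases what another refuses or demands, two sites can reach different decisions about the same man: whether he is eligible, what he is told to do, and for how long.

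Two things are at stake. The reproductive restrictions are one of the two protections that Table 2 relies on while developmental toxicity is unstudied, and criteria 7 and 9 are where they are spelled out for men. The recording of deviations also depends on the text. SAP Section 3.3.4 puts inclusion-criteria deviations first among the categories of important protocol deviation, and SAP Section 4.1.3.2 tabulates these by treatment group. Whether an abstinent man counts as such a deviation depends on which paragraph is read.

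**Working it through.** No plan figure is involved. The check is a comparison of the three paragraphs, plus calendar arithmetic from the Schedule of Activities (screening D-21 to D-1, first dose D1, final follow-up D99).

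| Element | 7(a) | 9(a) | 9(b) |
|---|---|---|---|
| Who is covered | Men | All men | Sterilised men |
| True abstinence | Not listed | Accepted | Not addressed |
| Barrier, non-sterile man | None stated | Added to the highly effective method | Not addressed |
| Barrier, sterilised man | None stated | Combined with vasectomy | Condom |
| Barrier if partner sterilised | Waived | No waiver; tubal ligation is on the list to be combined | Waived |
| Start | Consent | First dosing | First dosing |
| End | 3 months after final follow-up | 3 months after final follow-up | After final follow-up |

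Applying the paragraphs to four men:

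1. **Non-sterile, truly abstinent.** He meets 9(a). He is neither surgically sterile nor using a highly effective method, so read literally he fails 7(a). No conduct short of giving up his reliance on abstinence satisfies both.
2. **Vasectomised, partner not sterilised.** 7(a) is met with no condom stated. 9(a) combines vasectomy with a barrier until 3 months after final follow-up. 9(b) ends the condom after final follow-up. Taking 3 months as 91 days, 9(a) ends at about D99 + 91 = D190 and 9(b) at about D99, a gap of about 91 days.
3. **Non-sterile, partner has had tubal ligation.** 7(a) says that a barrier is unnecessary. 9(a) asks for one alongside that same method.
4. **Non-sterile, partner uses an IUD.** 7(a) requires the method from consent; 9(a) adds a barrier from first dosing; both end at the same time. The two can be followed together.

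The start dates differ by 1 day (consent on D-1) to 21 days (consent on D-21), since there is no Day 0. A man who complies from consent already complies from first dosing, so this is untidy but not a contradiction. The sperm-donation periods in 7(a), 9(c) and 8.3.10.2 all end 3 months after the last follow-up visit.

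**The case against.** The best case for the plan is that the criteria are cumulative, so the stricter wording governs. That disposes of the start date and of the added barrier for man 4, where 7(a) is merely silent. It does not settle the rest. For the abstinent man, the stricter wording excludes someone whom 9(a) expressly accepts. For men 2 and 3, doing more would satisfy every paragraph, but only by emptying 9(b)'s own end date and the waivers of meaning: one paragraph expressly releases the man from what another imposes.

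A reader can also harmonise. 7(a) speaks of a man acting with a female partner, and its list of methods is not stated to be exhaustive, so abstinence might be implied. 9(b) might be the special rule for sterilised men that displaces 9(a). Both readings are reasonable, but the protocol states neither, and 9(a) is addressed to all men. Criterion 8(a) does not count tubal ligation among permanent sterilisation procedures, which might narrow the third point; but that list concerns female participants, and 9(a) has no waiver for any sterilised partner.

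On safety, much of the objection stands. The requirement to be sterile, abstinent or using a highly effective method runs to 3 months after final follow-up in 7(a) and 9(a). A sterilised man remains sterile when his condom rule ends. Section 8.3.10.2 also provides for following partner pregnancies until 10 months after the last dose. The consent form is not in the material reviewed, so how men are actually counselled cannot be checked.

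**Conclusion.** The three contradictions are real: abstinence (7(a) against 9(a)), the barrier end date for sterilised men (9(a) against 9(b), about D190 against about D99, assuming 3 months is 91 days), and the waiver for a sterilised partner (7(a) and 9(b) against 9(a)). They should be corrected because they bear on eligibility, on instructions to participants and on what is recorded as a deviation.

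A reader might infer more than the text supports:

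- **That every male participant is affected.** The conflicts concern abstinent men, sterilised men and men with sterilised partners. The documents give neither a sex split nor the size of these groups. For non-sterile men, 7(a) and 9(a) share the same end date.
- **That the start date and the barrier for other non-sterile men are further contradictions.** Both can be met by following 7 and 9 together.
- **That the protection against reproductive risk fails.** Table 2 also relies on excluding women of childbearing potential, and the 3-month period for not fathering a child is stated consistently in 7(a), 9(a) and 8.3.10.2.

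This is an internal inconsistency. It has no effect on sample size, type I error or the efficacy analysis; SAP Section 3.3.4 says that important deviations do not remove participants from analysis sets unless otherwise specified.

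**What to change.** The sponsor should reconcile 7(a), 9(a) and 9(b) into a single male contraception criterion. It should have one list of accepted options that says whether abstinence is among them, one statement on barrier use that covers sterilised men and any waiver for a sterilised partner, one start and one end. Section 8.3.10.2 and the consent wording should be aligned with it. Which rule is right on each point is for the sponsor's clinical team.

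The cost is a text amendment to the inclusion criteria and any matching change to the consent form. Nothing in the design, sample size or analysis has to change.

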### **Informed Consent**

- 10 Capable of giving signed informed consent as described in Appendix A 3, which includes compliance with the requirements and restrictions listed in the ICF and in this protocol.
- 11 Provision of signed and dated, written ICF prior to any mandatory study specific procedures, sampling, and analyses. Participants who consent only to the main study may participate in other components of the main study without participating in the optional component of the study. However, to participate in the optional component of the study, the participant must sign and date both the consent forms for the main study and optional component of the study. If a participant declines to participate in the

optional component of the study, there will be no penalty or loss of benefit to the participant. The participant will not be excluded from other aspects of the study described in this protocol.

### **Other Inclusion Criteria**

Participants should refrain from blood donation throughout the study, including the follow-up period.

## **5.2 Exclusion Criteria**

Participants are excluded from the study if any of the following criteria apply:

### **Medical Conditions**

- 1 Estimated glomerular filtration rate (eGFR) < 45 mL/min/1.73m^2 using the Chronic Kidney Disease-Epidemiology Collaboration (CKD-Epi 2021(Age, Sex)) equation at Visit 1.
- 2 History or presence of gastrointestinal, hepatic or renal disease or any other conditions known to interfere with absorption, distribution, metabolism, or excretion of drugs.
- 3 Any uncontrolled or serious disease, or any medical (eg, known major active infection or major hematological, renal, metabolic, gastrointestinal, respiratory, or endocrine dysfunction) or surgical condition that, in the opinion of the investigator, may either interfere with participation in the clinical study and/or put the participant at significant risk.
- 4 Poorly controlled type 2 diabetes mellitus, defined as HbA1c > 10% at Visit 1.
- 5 Acute ischemic cardiovascular event in the last 12 months prior to randomization however patients can be included if it is > 6 months from coronary artery bypass graft surgery (CABG) surgery and > 3 months after percutaneous coronary intervention (PCI).
- 6 Heart failure with New York Heart Association (NYHA) Class III-IV.
- 7 Malignancy (except non-melanoma skin cancers, cervical in-situ carcinoma, breast ductal carcinoma in-situ, or Stage 1 prostate carcinoma) within the last 10 years.
- 8 Recipient of any major organ transplant, eg, lung, liver, heart, bone marrow, renal.
- 9 LDL or plasma apheresis within 12 months prior to randomization.
- 10 Uncontrolled hypertension defined as average sitting SBP > 160 mmHg or DBP > 90 mmHg at Visit 1. It is recommended that antihypertensive treatment should be considered/initiated at the PI's discretion and in accordance with applicable clinical guidelines in order to optimize blood pressure for participants with hypertension during the clinical study.
- 11 Heart rate after 10 minutes supine rest < 50 bpm or > 100 bpm at Visit 1.
- 12 Any laboratory values with the following deviations at Screening Visit 1; test may be repeated at the discretion of the investigator if abnormal:
  - (a) Any positive result on screening for hepatitis B, hepatitis C or HIV.

- (b) ALT > 1.5 × ULN
- (c) AST > 1.5 × ULN
- (d) TBL > ULN
- (e) Hemoglobin < 12 g/dL in men or < 11 g/dL in women
- (f) Potassium < LLN

13 Any clinically important abnormalities in rhythm, conduction or morphology of the resting ECG and any clinically important abnormalities in the 12 lead ECG as judged by the investigator including shortened QTcF < 340ms; family history of long QT syndrome; PR interval shortening < 120 ms; PR interval prolongation >220 ms, intermittent second or third degree AV block or AV dissociation; persistent or intermittent complete bundle branch block, incomplete bundle branch, or interventricular conduction delay with QRS > 110 ms.

14 QTcF > 450 ms; high degree atrioventricular-block grade II-III and sinus node dysfunction with significant sinus pause untreated with pacemaker; and cardiac tachyarrhythmias.

15 Known or suspected history of drug abuse as judged by the investigator.

16 History of alcohol abuse or excessive intake of alcohol as judged by the investigator.

17 History of severe allergy/hypersensitivity or ongoing clinically important allergy/hypersensitivity, as judged by the investigator or history of hypersensitivity to drugs with a similar chemical structure.

18 Any clinically important illness, medical/surgical procedure or trauma within 4 weeks of the first administration of study intervention. History or evidence of any other clinically significant disorder (eg, cognitive impairment), condition, or disease other than those outlined above that, in the opinion of the investigator or Sponsor physician, if consulted, may compromise the ability of the participant to give written informed consent, would pose a risk to participant safety, or interfere with the study evaluation, procedures, or completion.

